#### **4.6 Study Termination**

The Principal Investigator, [name], MPH, FACS, may discontinue the study at any stage.

#### **5.0 Assessment of Time-in-Range (TIR)**

TIR is calculated as the number of points in range divided by the total number of measurements presented. When the smart alarm is active, readings during that period are excluded from the calculation.

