### **1.5 Risks and Benefits**

There have been no serious adverse events related to the OptiScanner in any of the clinical studies performed to date.

Risk management in accordance with EN 14971, was completed on the study device. The conclusion is that the OptiScanner has an acceptable safety profile.

Because the OptiScanner system delivers automated, every 15 minutes glucose results and trends, it has the potential to improve a patient's glucose TIR by providing earlier identification of abnormal glucose values that would otherwise remain unknown until the clinical care scheduled glucose value was obtained (which typically are collected every 1 to 4 hours, depending on the condition of the patient). Therefore, the OptiScanner has the potential to improve all 3 domains of glycemic control: reducing hyperglycemia while at the same time preventing hypoglycemia and reducing glycemic variability. In the future, the OptiScanner may also reduce the workload associated with the high number of blood samples to be obtained and analyzed [22, 26-29].

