#### **4.2.2 Phase Two**

Following the 1st phase of the trial, data on time-in-range and patient glucose management activities and responsiveness to insulin adjustments will be assessed by the PI, a statistician, OptiScan and potentially, ICU nursing and physician leadership. Phase II Study procedures will be developed based on the results.

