#### **4.3.2 Additional Data Collected**

The following data will be collected during the OptiScanner evaluation:

- Demographic Data
- Date of admission
- Primary and secondary diagnosis
- History of thromboembolic events and clotting disorders
- Medications administered during ICU stay
- Insulin administration: timing, dosage, route and protocol used
- Insulin adjustment: reason for the adjustment, OS glucose value prior to insulin adjustment and standard of care confirmatory glucose value obtained if adjustment was related to an abnormal OS glucose value, timing of insulin adjustment, dosage, and route
- Dextrose administration/IV: timing, and dosage
- Dextrose adjustment: reason for the adjustment, OS glucose value prior to insulin adjustment and standard of care confirmatory glucose

value obtained if adjustment was related to an abnormal OS glucose value, timing of dextrose adjustment, dosage, and route

- TPN and other nutrition
- TPN and other nutrition adjustment
- Number of Hypoglycemic events (defined as glucose < 70 mg/dL)
- Number of Hyperglycemic events (defined as glucose > 200 mg/dL)
- Ventilator days, ICU LOS, and HLOS
- Infection outcome data
- Procedures including imaging, dialysis, and transfusions
- Date and time of OS connection/disconnect
- Contrast administration
- Discharge disposition (i.e. home, rehab, nursing home, death, etc.)
- Device related AE's and SAE's

Additional data not typically collected in the patient's medical records:

- Types and frequency of alarms (both dysglycemia and others) downloaded from the OptiScanner after the case
- The frequency of CVC maintenance incidents requiring disconnection from the OptiScanner system
- Comparator measurements (at the start, at approximately 24-hour intervals, and when prompted by the OptiScanner (i.e. cartridge change) Patients will have a study blood draw after OptiScanner connection, at approximately 24-hour intervals, and when prompted by the OptiScanner (i.e. cartridge change). The sample may be point of care or sent to the laboratory for analysis.
- History of CVC line (occlusions, other clotting disorders, age, etc)
- Clinical care team action/inaction details related to all glucose values (both OptiScanner and standard of care values).

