#### 4.3.3 Safety Endpoint

The proportion of subjects that experience one or more Device Related Serious Adverse Events (DRSAEs). Incidence of hypo/hyperglycemia.

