**7.0 Statistics**

For Phase One of this study, no formal statistics will be performed as this phase is strictly observational. Results of Phase One will be used to inform the power analysis for the 2nd phase of the study.

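### Primary TIR leaves out all readings taken under an undefined smart alarm; report TIR with and without the exclusion and state what triggers the alarm

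*Protocol*

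**What the plan says.** Section 4.3.1 of the protocol makes glucose TIR the primary endpoint. Section 5.0 defines it: "TIR is calculated as the number of points in range divided by the total number of measurements presented". The next sentence restricts the readings that count: "When the smart alarm is active, readings during that period are excluded from the calculation". The restriction has no exceptions, and no second TIR that keeps these readings is planned.

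The smart alarm is not mentioned outside section 5.0. What starts it, what ends it and how long it lasts are not given. The nearest related text is in section 4.3.2 (Additional Data Collected), which lists "Types and frequency of alarms (both dysglycemia and others) downloaded from the OptiScanner after the case". That shows two classes of alarm but does not place the smart alarm in either. Section 11.0 asks for every device alarm to be kept in the subject's record, without mentioning times.

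Section 8.0 says that the device stores all glucose data, that these are downloaded for analysis, and that the device itself computes a percent-in-range figure. It does not say whether that figure applies the exclusion.

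On the use of the result, section 4.2.2 says that after Phase One "data on time-in-range and patient glucose management activities and responsiveness to insulin adjustments will be assessed by the PI" and others, and that Phase Two procedures follow from this. Section 7.0 plans no formal statistics for Phase One, but says: "Results of Phase One will be used to inform the power analysis".

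**The concern.** TIR is a proportion of readings, so it depends on which readings are counted. A rule that drops readings for a reason unrelated to glucose costs some precision and nothing else. A rule that drops them because glucose is, or is heading, out of range removes part of what TIR is meant to measure. The protocol fixes the exclusion without saying which kind of rule it is. Because the device has dysglycemia alarms, the second kind cannot be dismissed from the text.

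The direction of any bias is also open. An alarm that sounds while glucose is out of range would remove mainly out-of-range readings and raise TIR. An alarm that predicts a coming excursion could remove readings that are still in range and lower it.

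At stake are a descriptive primary result and its use in planning Phase Two. No type I error or power statement in Phase One is affected, because there is none.

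**Working it through.** The protocol states no expected TIR, alarm frequency or alarm duration, so there is no figure to reproduce. The calculation below only bounds what the exclusion could do.

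**Inputs from the protocol**
- One reading every 15 minutes (section 1.5: "Because the OptiScanner system delivers automated, every 15 minutes glucose results and trends"), that is 4 per hour.
- 48 to 72 hours of monitoring (section 4.5). If no cycle is lost, N = 4 × 48 = 192 or N = 4 × 72 = 288 readings.

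**Assumed inputs**
- p, the TIR on all readings including those under the alarm: 60%, 70% or 80%.
- k, the readings excluded: 2 hours under the alarm, k = 4 × 2 = 8.

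**Formulas**
- Lower bound, all excluded readings in range: (pN − k)/(N − k).
- Upper bound, all excluded readings out of range: pN/(N − k).
- If excluded and kept readings have the same in-range share, reported TIR equals p and the bias is zero.

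**Results with k = 8**

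| N | p | Lower bound | Upper bound |
|---|---|---|---|
| 192 | 60% | 107.2/184 = 58.3% | 115.2/184 = 62.6% |
| 192 | 70% | 126.4/184 = 68.7% | 134.4/184 = 73.0% |
| 192 | 80% | 145.6/184 = 79.1% | 153.6/184 = 83.5% |
| 288 | 70% | 193.6/280 = 69.1% | 201.6/280 = 72.0% |

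**Exclusion needed for a 5-point shift at p = 70%**, with f = k/N:
- Upward, all excluded readings out of range: pf/(1 − f) = 0.05, so f = 0.05/0.75 = 6.7%. In 48 hours that is 12.8 of 192 readings, or 3.2 hours.
- Downward, all excluded readings in range: (1 − p)f/(1 − f) = 0.05, so f = 0.05/0.35 = 14.3%. In 48 hours that is 27.4 of 192 readings, or 6.9 hours.

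**Larger exclusions.** With f = 10% and p = 70%, the bounds are (0.70 − 0.10)/0.90 = 66.7% and 0.70/0.90 = 77.8%, whatever N is.

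A short alarm period can therefore move an individual patient's TIR by only a few points, even in the extreme cases. A period of several hours could move it materially. The protocol does not say which to expect.

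**The case against.** The strongest reply is that the protocol shows no bias. The smart alarm is presumably a function of a cleared device, its trigger would be described in device documentation that is not at hand, and a technical flag would make the exclusion correct. That stands: selection on the outcome cannot be asserted. It does not remove the point, because the protocol commits to the exclusion whatever the trigger is and plans no TIR beside it.

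Three stronger readings are tempting and should not be drawn.

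- *The rule must discard results that the device displayed, because the denominator is already limited to presented measurements.* The sentence on the smart alarm may instead clarify which readings count as presented. If no value is presented during an alarm, the two versions of TIR coincide.
- *Any trigger that uses the glucose value makes the exclusion improper.* A validity check may use the glucose value, for instance to reject an implausible jump, and still remove only bad measurements.
- *The exclusion contradicts the event counts.* Section 4.3.2 counts hypoglycemic and hyperglycemic events (the first item reads "Number of Hypoglycemic events (defined as glucose < 70 mg/dL") and section 4.3.3 lists "Incidence of hypo/hyperglycemia", both without this exclusion. Neither states the glucose source. Only if it is the OptiScanner could one reading count as an event and be absent from TIR, and even then different measures may use different sets of readings.

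It is also fair to say that section 5.0 may describe the device's built-in calculation (section 8.0) rather than an analyst's choice. That affects where the rule comes from, not its effect on TIR. Finally, Phase One has no formal test, the glucose data are retained, and Phase Two is still to be designed with a statistician's input. This limits the severity.

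**Conclusion.** The point holds in a limited form. The only formula for the primary endpoint contains an unconditional exclusion tied to an undefined alarm, and no TIR that includes those readings is planned. The device has dysglycemia alarms, so selection on the outcome is possible. It is not established, and its direction is unknown.

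With 2 hours excluded in 48, an assumed TIR of 70% would be reported as something between 68.7% and 73.0%. Over assumed values of 60% to 80%, the largest shift is about 3.5 points (80% to 83.5%). These figures rest on assumed TIR and alarm duration and on the extreme cases in which all excluded readings fall on one side. If the alarm only flags invalid measurements, there is no error to correct.

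The consequence is a possibly distorted descriptive TIR and a possibly distorted input to Phase Two planning. Severity is minor, and the change is a cheap improvement.

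**What to change.** In section 5.0:

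1. Calculate TIR from the downloaded readings both with and without the smart-alarm exclusion, wherever a glucose value exists for the alarm period. Report the number of readings and hours excluded per patient.
2. State what starts and ends the smart alarm, and whether the device's own percent-in-range figure (section 8.0) applies the exclusion. The two calculations show how much the rule matters; only the definition shows whether it selects on glucose.
3. Let the definition decide the primary version. Keep the exclusion if the alarm flags invalid measurements, including by a check that uses the glucose value. If it signals actual or predicted dysglycemia, make TIR on all valid readings primary.

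In section 4.3.2 (Additional Data Collected), add alarm start and end times. The list now names only types and frequency, and without times neither the stated rule nor the count of excluded hours can be checked from the download.

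Carry both TIR versions into the Phase Two assessment and power analysis.

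The cost is a few sentences, one extra calculation, and the capture of alarm times if these are not already downloaded. No extra patients or procedures are needed. The reported TIR may turn out less favourable.

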#### **6.0 Assessment of Safety**

The rate of Device-Related Serious Adverse Events (DRSAEs). The relationship of the event to the study device and whether the event is considered serious will be determined by the Investigator.

**7.0 Statistics**

For Phase One of this study, no formal statistics will be performed as this phase is strictly observational. Results of Phase One will be used to inform the power analysis for the 2nd phase of the study.

**8.0 Data Management**

The Investigator is responsible for the development of appropriate case report forms. The Investigator will be responsible for the accurate and timely collection of data during the study. Quality assurance procedures will be established to ensure that complete, accurate and timely data are collected, that protocol requirements are followed, and that complications, adverse events and adverse device effects are correctly reported and investigated, as appropriate. The Investigator and site CRC will maintain all source documents as required by the protocol, supporting medical records, and signed Informed Consent Forms. All glucose data will be stored within the OptiScanner and will be downloaded for data analysis purposes and the electronic files will be submitted to the Investigator. The OptiScanner calculates percent in range.

**9.0 Investigator Responsibilities**

The Investigator is responsible for ensuring that this study is conducted according to this protocol and that a signed approved Informed Consent Form is obtained from each patient prior to their inclusion in this study. The Investigator will also ensure that all staff assisting with this study have the appropriate qualifications and are fully instructed on the study procedures and respect patient confidentiality, as specified in the Health Insurance Portability and Accountability Act (HIPAA) requirements.

The Investigator is responsible for ensuring that the conduct of this study conforms to with his or her IRB/EC requirements and provides all necessary communication with the IRB/EC including, but not limited to, annual study reports and required AE notifications.

The Investigator and study staff should make every possible effort to ensure that complete data is obtained for each study patient.

**10.0 Ethics**

**10.1 Study Conduct**

The study will be performed in accordance with the relevant parts of the U.S. Code of Federal Regulations (including 21 CFR parts 50, 54, 56 and 812), ICH Guidelines for Good

Clinical Practices, the European Standard ISO 14155, the Declaration of Helsinki, and any regional and/or national regulations.

## **10.2 Ethics Review**

Before any subject can be enrolled in this study, the IRB or EC for the specific institution must review and approve this protocol.

## **10.3 Informed Consent**

Informed consent will be required

## **11.0 Data Handling and Record Keeping**

The Investigator must maintain detailed source documents on all subjects who are enrolled in the study. Source documents include medical records, hospital charts, clinic charts, Investigator study files, as well as the results of diagnostic tests (e.g., medication records, laboratory tests, hemodynamic studies).

The following minimum information should be entered into the subject's study and/or medical record:

- The date of enrollment and study ID
- The study protocol name and number
- Documented eligibility requirements (e.g., medical history, study procedures and/or evaluations)
- The duration of study participation
- Evidence that required evaluations were completed
- Use of any concurrent medications during study enrollment, and where infused
- Transfusions or Dialysis
- Documentation of specific device used
- Occurrence and status of any adverse events that in the Investigator's opinion are related to the OptiScanner
- All OptiScanner alarms
- The date the subject exited the study and a notation as to whether the subject completed the study or was discontinued, including the reason for discontinuation
- The insulin, dextrose, and nutrition administration delivery

## **12.0 Training and Case Support**

### **12.1 Investigational Site Training**

To ensure appropriate and reliable use of the OptiScanner system, OptiScan Biomedical (manufacturer) will provide didactic and hands-on training for all designated users.

OptiScan Biomedical will outline an installation and continuous education program that is adequate for the hospital's SICU predefined users.

All device training will be documented in a training log that will be maintained in the site regulatory binder.

## **12.2 Clinical Case Technical Support**

OptiScan Biomedical will assign a cross-functional team with clinical expertise to conduct training and support the SICU's clinical staff with any device related technical questions during all cases conducted in this study.

## **13.0 Adverse Events and Serious Adverse Events**

It is anticipated that subjects in this study will experience a large number of adverse events associated with their underlying condition, which have no relationship to the study device. Therefore, for this study, Investigator will record only Adverse Events (AEs) that, in the Investigator's opinion, are possible, probably or definitely related to the study device. All such events must be recorded in the patient study and/or medical record. A description of the event, including the start date, resolution date, action taken, and the outcome should be recorded, along with the Investigator's assessment of the relationship between the event and the OptiScanner device.

